9.1.3 Severity of adverse events

The incidence rates (%) and event counts of severe TEAEs by SOC and by PT will be summarized by treatment group in Table 14.3.1.8.

Table 14.3.1.9 will summarize the incidence rates (%) of severe TEAE PTs, sorted by descending incidence of PT in the active drug group.

Counts of drug-related TEAEs in the active drug group will be summarized by severity, SOC and PT in Table 14.3.1.10. Similarly, counts of drug-related TEAEs in the placebo group will be summarized by severity, SOC and PT in Table 14.3.1.11.

9.1.4 Comparisons between those with and without a drug-related AE

Table 14.3.1.12 will provide a comparison of demographic and baseline disease characteristics between actively treatment patients experiencing and not experience at least one drug-related adverse event. This table will only be included if there are at least 5 subjects with at least one drug-related adverse event.

9.1.5 Day 0 Adverse Events

Table 14.3.1.13 provides a summary of specific adverse events occurring prior to study drug initiation. This table is not stratified by drug group.

9.1.6 Adverse Events of Special Interest

Infection and infestation adverse events are of special interest. Table 14.3.1.14 summarizes the incidence rates and event counts for infections and infestations TEAEs by preferred term.

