- To demonstrate efficacy of AB103 in relation to the critical care and hospital stay parameters:
 - a. ICU days
 - b. ICU-free days
 - c. Days on ventilator
 - d. Ventilator free days
 - e. Vasopressor days
 - f. Vasopressor free days
 - g. Hospital length of stay
- To demonstrate the efficacy of AB103 in patients with septic shock
- To determine the incidence of Stage 2 and 3 acute kidney injury (AKI) (using the KDIGO criteria) and compare the rates of complete recovery by Day 28 between the AB103 treated patients and the placebo treated patients
- Additional AKI endpoints:
 - To determine the incidence of Stage 2 and 3 AKI (using the KDIGO criteria) and compare the rates of complete and partial recovery by Day 28 between AB103 and placebo treated patient
 - Determine the incidence of Stage 1, 2 and 3 AKI and compare the rates of complete recovery between the AB103 and placebo treated patients
 - Determine the incidence of Stage 1, 2 and 3 AKI and compare the rates of complete and partial recovery between the AB103 and placebo treated patients
 - Calculate time to complete recovery from AKI
 - Calculate time to partial recovery from AKI
- To demonstrate the safety of AB103 in regard to secondary infections

2.3 Exploratory Objectives:

- To conduct an exploratory evaluation of the clinical response by baseline pathogen
- To evaluate microbiological outcome in the microbiological evaluable population
- To conduct an exploratory evaluation of plasma and urinary biomarkers in patients with AKI
- To conduct an exploratory evaluation of blood leukocyte transcriptome (RNA expression) profiling in patients with NSTI and compare genomic profile in patients treated with AB103 versus placebo
- To evaluate health economic and financial outcomes associated with the treatment
- To evaluate NICCE outcome in screen failure patients with baseline mSOFA = 2 and post-operative mSOFA \ge 3. Note: These patients will not be included in the

MITT population analysis (they will not receive blinded study drug) and only considered to be an observational cohort

• To evaluate the immunogenicity of Reltecimod (formerly AB103)

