4.3.5 Visit 5 (Day7 [±1 day])

- Collect data on operative procedures
- Collect data on acute renal replacement therapy
- Collect data on plasma or platelet transfusion
- Urine output (should be recorded continuously from time of ICU admission to Day 7, if still in ICU and Foley catheter in place, using 6 hour intervals and by calendar day)
- Weight (if easily obtained)
- Collection of AEs/ SAEs including secondary infections (based on CDC definitions for healthcare associated infections)
- Collect data on additional amputations
- Concomitant medications
- Vital signs (to be taken during the morning tests)
- **P**E
- Safety laboratory tests (Chemistry, Hematology)

- Sample for CBC with differential and platelet count can be same as that required to be taken in conjunction with the RNA expression profile test sample
- Assess lesion status (healing/progression/significant change in appearance) if accessible for visible assessment at time of debridement or routine dressing change
- Critical care parameters (dates and times of assisted ventilation, vasopressor use, ICU /hospital stay)
- Systemic response: collect data for mSOFA parameters
 - All efforts should be made to obtain the actual measurements of SOFA parameters at these visits-may use SpO2 value (and record FiO2) if arterial blood gas is not clinically indicated.
- Collect urine and blood for plasma for storage (AKI biomarker analysis)
- Collect whole blood for leukocyte transcriptome (RNA expression) profiling
 - CBC with differential required to be obtained in conjunction with sample for RNA expression profile best
- Record Survival

4.3.6 Visit 6 (Day 10 [±1 day]; perform only if patient is still hospitalized):

- Collect data on operative procedures
- Collection of AEs/SAEs, including secondary infections (based on CDC definitions for healthcare associated infections)
- Collect data on additional amputations
- Collect data on acute renal replacement therapy
- Collect data on plasma or platelet transfusion
- Selected concomitant medications (e.g. vasopressors, antimicrobials)
- Symptom-driven interim PE
- Vital signs
- Critical care parameters (dates and times of assisted ventilation, vasopressor use, ICU /hospital stay)
- Systemic response: collect data for mSOFA parameters
 - All efforts should be made to obtain the actual measurements of SOFA parameters at these visits-may use SpO2 value (and record FiO2) if arterial blood gas is not clinically indicated
 - Obtain serum creatinine

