4.3.8 Visit 8 (Day 21 [±1 day])

- Collection of AEs/SAEs, including secondary infections (based on CDC definitions for healthcare associated infections)
- Collect data on additional amputations
- Collect data on acute renal replacement therapy
- Collect data on plasma or platelet transfusion
- Selected concomitant medications (e.g. vasopressors, antimicrobials)
- Critical care parameters (dates and times of assisted ventilation, vasopressor use, ICU /hospital stay)
- Vital Signs
- Systemic response: collect data for mSOFA parameters
 - All efforts should be made to obtain the actual measurements of SOFA parameters at these visits-may use SpO2 value (and record FiO2) if arterial blood gas is not clinically indicated
 - Obtain serum creatinine
 - Obtain CBC and platelet count (differential not required for Day 21)

• Record Survival

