8.3 Reporting of Adverse Events

All AEs that occur between randomization through Day 28 visit will be reported. AEs that start prior to study drug administration will also be captured. Worsening signs and symptoms of the underlying disease will be reported as AEs.

The course of each event should be followed until resolution. All unresolved AEs should be followed-up by the Investigator until the events are resolved, or the AE is stabilized and otherwise explained.

AEs should be recorded according to findings and abnormalities detected by the Investigator. Specific capturing of potential secondary infections will take place. In addition, patients should report AEs voluntarily and in response to general, non-directed questioning. For each AE reported by the patient, or observed by the Investigator, the Investigator should obtain all the information required to complete the AE page of the eCRF, in accordance with the guidelines that accompany it.

Atox Bio or designee assumes responsibility for appropriate reporting of SAEs to the regulatory authorities. Atox Bio or designee will also report to the Investigators all SAEs that are unexpected and associated with the use of the drug.

The Investigator must report these events to the appropriate IRB/IEC in accordance with local regulations.

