8.4 Reporting of Serious Adverse Events

All SAEs occurring with any patient participating in this clinical study must be recorded. All SAEs must be reported within 24 hours of becoming aware of the event to the Sponsor or designee, with the exception of SAEs that are specifically attributed to underlying disease (see section 8.5). All SAEs beginning within 28 calendar days after the last exposure to IMP must be recorded.

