8.5.1 List of Expected Adverse Events

Acute respiratory failure; respiratory distress; acute lung injury; acute respiratory distress syndrome (ARDS); acute renal failure; coagulation dysfunction; decreased platelet count; neutropenia; hypothermia; fever, bacteremia; sepsis, septic shock; hypotension; metabolic acidosis, pleural effusion; abdominal compartment syndrome; repeated surgeries/debridement; amputation.

For purposes of this study, deaths will be captured as clinical outcomes and do not need to be reported as SAEs unless felt related to study drug administration.

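### The secondary-infection safety objective has no analysis of its own: infection TEAEs are tabulated by preferred term without separating the index NSTI from new infections

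*SAP*

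**What the plan says.** **Objective and collection.** Protocol 2.2 lists as a secondary objective: "To demonstrate the safety of AB103 in regard to secondary infections". Protocol 8.1 counts secondary infections among the primary safety measures. Protocol 8.3 adds: "Specific capturing of potential secondary infections will take place". The visit schedules in Protocol 4.3.4 to 4.3.8 (Days 3, 7, 10, 14 and 21) ask for them under CDC definitions of healthcare-associated infection. The Day 29 visit (4.3.9) asks for them without mentioning CDC. Protocol 5.2.2.1 also has sites record whether each antimicrobial was given for the primary infection, a secondary infection or prophylaxis.

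**Analysis.** Protocol 9.3 promises summaries of AEs and SAEs in the infection system organ class. SAP 6 lists the safety measures without secondary infections. SAP 9.1.6 gives the one dedicated analysis: "Table 14.3.1.14 summarizes the incidence rates and event counts for infections and infestations TEAEs by preferred term". Under SAP 6.1 and 9.1.1, TEAEs run from Day 1 to Day 28. The AE listings in SAP 9.1.7 carry class, term, relationship, severity, dates and action, but nothing that marks a secondary infection. No form named for secondary infection appears among the listings in SAP Appendix 3.

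**What else falls in the class.** Protocol 8.3 states: "Worsening signs and symptoms of the underlying disease will be reported as AEs". Protocol 8.5 says that common disease-related abnormalities need not be AEs unless certain conditions apply. The list in 8.5.1 of events that may accompany the initial NSTI includes "neutropenia; hypothermia; fever, bacteremia; sepsis, septic shock".

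**The concern.** AB103 attenuates CD28 signalling, so whether treated patients acquire more new infections is a natural safety question, and the protocol asks it. The trial also hypothesises that the drug improves the local and systemic course of the index infection. If that is right, index-related infection events should fall. A summary that combines index events with new infections then combines two quantities that may move in opposite directions.

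Splitting by preferred term does not supply the missing quantity. It spreads secondary infections over many small rows, and a patient may appear in several. The rows cannot be added to give the number of patients with at least one secondary infection. A row headed sepsis or bacteremia does not say which infection caused it.

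The stakes go beyond this study report. SAP 1.1 says that ATB-202 will form the bulk of the safety population for the NDA, so another trial may not be able to fill the gap.

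**Working it through.** The documents give no rate, margin or power for secondary infection, so there is no figure of the plan's own to reproduce. All infection rates below are assumptions. It is also assumed that sepsis, septic shock and bacteremia code to the infection class, since the documents do not give the coding.

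**1. Following the plan as written.** The objective needs patients with at least one secondary infection, by arm. SAP 9.1.2 gives TEAEs, drug-related TEAEs and serious TEAEs by class and/or term; 9.1.3 does the same for severe TEAEs; 9.1.6 gives infection TEAEs by term. None is restricted to secondary infections. This step needs no assumed rate.

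**2. Size of the masking in a class total.** Let a be the proportion of patients with an index-related infection TEAE and s the proportion with a secondary infection, taken as independent. The proportion with any infection TEAE is

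c = 1 − (1 − a)(1 − s).

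Take s = 15% on placebo and 30% on drug, with a halved on drug:

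| a, placebo → drug | c, placebo | c, drug | Difference (points) |
|---|---|---|---|
| 5% → 2.5% | 19.3% | 31.8% | +12.5 |
| 10% → 5% | 23.5% | 33.5% | +10.0 |
| 20% → 10% | 32.0% | 37.0% | +5.0 |
| 30% → 15% | 40.5% | 40.5% | 0 |
| 40% → 20% | 49.0% | 44.0% | −5.0 |

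For the fourth row, placebo is 1 − 0.70 × 0.85 = 0.405 and drug is 1 − 0.85 × 0.70 = 0.405. For the second row, placebo is 1 − 0.90 × 0.85 = 0.235 and drug is 1 − 0.95 × 0.70 = 0.335.

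**3. What full masking requires.** Setting the two totals equal gives the index rate on drug at which the rise disappears:

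a(drug) = 1 − (1 − a(placebo)) × 0.85 / 0.70.

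- a(placebo) = 40%: a(drug) = 27.1%, a relative reduction of 32%.
- a(placebo) = 30%: a(drug) = 15.0%, a reduction of 50%.
- a(placebo) = 20%: a(drug) = 2.9%, a reduction of 86%.
- a(placebo) = 10%: a(drug) would be negative, so full masking is impossible.

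For a smaller rise, 15% to 25%, the reductions needed are 20%, 31% and 53% at 40%, 30% and 20%. At 10% full masking is again impossible.

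**4. Dilution without any drug effect on index events.** If a is 30% in both arms, the class difference is (1 − 0.30) × (0.30 − 0.15) = 10.5 points instead of 15.

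**5. Precision.** With the planned 145 per arm, a separate table at 15% vs 30% has a 95% half-width of 1.96 × √(0.15 × 0.85/145 + 0.30 × 0.70/145) = 9.5 points, so the difference is 15.0 (5.5 to 24.5). The diluted contrast of 23.5% vs 33.5% has a half-width of 1.96 × √(0.235 × 0.765/145 + 0.335 × 0.665/145) = 10.3 points, so it is 10.0 (−0.3 to 20.3).

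**The case against.** The strongest reply is that the table is broken down by preferred term. A new infection with its own term, such as a pneumonia, has its own row by arm, and fewer index events cannot cancel it. That is correct. Masking is confined to class totals and to terms that can describe either infection.

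Other limits also stand. Events before dosing are excluded from TEAEs and shown separately as Day 0 events (SAP 9.1.5). Protocol 8.5 keeps some index-disease events out of the AE data. Serious and severe TEAEs are tabulated too, and the listings give onset dates, cultures and antimicrobials. SAP 6 plans descriptive safety comparisons, so what could be masked is a descriptive contrast rather than a test result. The iDMC already receives unblinded safety data by group (Protocol 8.7).

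These points narrow the problem without removing it. None of these outputs counts patients with a secondary infection. A reader could try to rebuild that count from listings, but only after unblinding and by unstated rules. Protocol 8.3 and 8.5 also pull in different directions, so the documents do not fix how much index disease enters the class.

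**Conclusion.** The point holds as a gap in the analysis. A stated safety objective, with data collected for it, has no table that answers it. That rests on the documents alone.

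The size of any masking rests on assumed, independent rates. For a rise from 15% to 30%, it ranges from slight (12.5 of 15 points still visible when index events are 5% and halved) to complete (30% and halved) or reversed (40% and halved).

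Three stronger readings are tempting and not supported:

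- **That infections are analysed only as one undivided class, so a rise would be cancelled.** The preferred-term rows contradict the first part, and the table above shows that cancellation happens only at particular rates.
- **That secondary infection is an established risk of the drug.** Protocol 1.2 says no specific drug-related safety concern has been identified; the protocol states an objective.
- **That septic shock from a new organism may skip 24-hour SAE reporting because septic shock is listed in 8.5.1.** The exemption in Protocol 8.4 reads "with the exception of SAEs that are specifically attributed to underlying disease (see section 8.5", and 8.5 ties its list to the initial NSTI, so a new infection is not clearly covered. What does stand is an inconsistency: 8.4 has an exemption, while 8.4.1 asks for the SAE screens within 24 hours without one.

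**What to change.** **SAP 9.1.6.** Add a table in the As Treated set of patients with at least one secondary infection by the collected CDC-based classification, by arm, with the risk difference and 95% CI. State the onset window, because TEAEs start on Day 1 and CDC-based collection on Day 3. Take death into account, for example with a rate per patient-day alive to Day 28, since a patient who dies early has less time to acquire an infection. Show serious and bacteremic secondary infections as sub-rows, and index-NSTI events separately. Keep Table 14.3.1.14 as it is. Supply the new table to the DMC.

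**Before finalising.** The sponsor should confirm that the classification is held in the database. Protocol 8.3 implies a site-level record, but the listed forms do not show one. The antimicrobial reason (Protocol 5.2.2.1), onset dates and culture results can serve as supporting sources.

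**Protocol.** Reconcile 8.3 with 8.5 on whether worsening of the index disease is an AE, and 8.4 with 8.4.1 on 24-hour SAE reporting. In both places, state how secondary infections are handled.

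**Cost.** One more table and short clarifying text. If the classification is in the database, no new data collection is needed. If it is not, secondary infections would have to be classified from the supporting sources under blinded rules set before unblinding, which is more work.

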9.1.7 Safety listings

The following listings will be provided for all patients in the Safety Analysis Set. Adverse event listings will include SOC, PT, relationship, severity, onset and resolution dates, and action taken.

		AE Listings
1	16.2.7.1	All TEAEs Sorted by Specific AE: Day1+ by Treatment Group, Sorted by SOC and PT As Treated (Safety) Analysis Set
2	16.2.7.2	All TEAEs Sorted by Specific AE: Day1+ by Treatment Group, Sorted by Patient ID and Onset As Treated (Safety) Analysis Set
3	16.2.7.3	Drug-Related TEAEs Sorted by Specific AE: Day1+ by Treatment Group, Sorted by SOC and PT As Treated (Safety) Analysis Set

		AE Listings
4	16.2.7.4	Serious TEAEs Sorted by Specific AE: Day1+ by Treatment Group, Sorted by SOC and PT As Treated (Safety) Analysis Set
5	16.2.7.5	Serious Drug-Related TEAEs Sorted by Specific AE: Day1+ by Treatment Group, Sorted by SOC and PT As Treated (Safety) Analysis Set
6	16.2.7.6	All TEAEs with Outcome of Death Sorted by Specific AE: Day1+ by Treatment Group, Sorted by SOC and PT As Treated (Safety) Analysis Set
7	16.2.7.7	All TEAEs with Outcome of Drug-Related Death Sorted by Specific AE: Day1+ by Treatment Group, Sorted by SOC and PT As Treated (Safety) Analysis Set
8	16.2.7.8	All TEAEs with Outcome of Study Drug Discontinuation Sorted by Treatment Group, SOC, and PT As Treated (Safety) Analysis Set
9	16.2.7.9	All TEAEs with Outcome of Discontinuation from Study Sorted by Treatment Group, SOC, and PT As Treated (Safety) Analysis Set

9.2 Clinical Laboratory Assessments

9.2.1 Blood Chemistry

Table 14.3.2.1 summarizes the values and changes from screening (baseline) for each of 15 tests included in the chemistry panels at Screening, Day 7 and Day 14.

Table 14.3.2.2 provides a shift table summarizing the numbers and percentages of patients going from a normal blood chemistry value to a normal, low or high value at Day 7; going from a low baseline blood chemistry value to normal, low or high at Day 7; and going from a high baseline blood chemistry value to normal, low or high at Day 7. The percentages presented in this table correspond to each baseline status. For example, the one of the reported percentages will indicate the percentage of subjects that started with a normal value but ended with a high value. This will be done separately for each treatment group.

Table 14.3.2.3 provides the same information but for shifts to Day 14.

9.2.2 Hepatic Safety

The chemistry data will be evaluated for any cases of Hy's Law or Drug Induced Liver Injury (DILI). These were defined as patients with ALT more than 3 X ULN, Total Bilirubin >2 X ULN with a normal Alkaline Phosphatase. Table 14.3.2.4 summarizes these results.

9.2.3 Blood Hematology

Similarly, Table 14.3.3.1 summarizes the values and changes from baseline for each of the 15 tests included in the hematology panels at Screening baseline, Day 1, Day 2, Day 3, Day 7, and Day 14 by treatment group.

Table 14.3.3.2 provides a shift table summarizing the numbers and percentages of patients going from a normal blood hematology value to a normal, low or high value at Day 7; going from a low baseline blood hematology value to normal, low or high at Day 7; and going from a high baseline blood hematology value to normal, low or high at Day 7. The percentages presented in this table correspond to each baseline status. For example, one of the reported percentages will indicate the percentage of subjects that started with a normal value but ended with a high value. This will be done separately for each treatment group.

Table 14.3.2.3 provides the same information but for shifts to Day 14.

9.3 Vital Signs

Baseline height (cm), weight (kg), and BMI (kg/m²) are summarized for the As Treated (Safety) analysis set in the Demographics and Baseline Disease Characteristics, Table 14.1.2.2.

The following vital sign variables are summarized by treatment group at screening and then at Days 1, 2, 3, 7, 14, 21, and 28 in Table 14.3.5.1. For follow-up visits, changes from screening are also summarized: Weight (kg), Temperature (Celsius), Systolic BP (mmHg), Diastolic BP (mmHg), MAP, Respiratory Rate (breaths/min), and Heart Rate (beats/min).

9.4 Electrocardiogram

Table 14.3.6.1 summarizes ECG results at screening and immediately, 4-6 hours, and 12-24 hours post study drug, and changes from screening by treatment group based on investigator provided results.

Table 14.3.6.2 provides the same summary but based on the cardiology central reader.

Table 14.3.6.3 summarizes the number and percentages of patients meeting threshold criteria for QTc ECG evaluations by the investigator in the As Treated (Safety) analysis set.

Table 14.3.6.4 provides the same summary for QTcB ECG evaluations determined through cardiology central reader.

Table 14.3.6.5 provides the same summary for QTcF ECG evaluations determined through cardiology central reader.

9.5 Physical Examinations

Physical exam results will be summarized for the screening visit, Day 3, Day 7 and at Day 14. For each test, the number of patients evaluated, and the numbers and percentages of patients with 'Normal', 'Abnormal, improved or same as screening', 'Abnormal, new or aggravated' and 'Not done' will be tabulated, except for screening when results will be categorized as 'Normal', 'Abnormal' or 'Not done'. Results for the following assessments will be summarized for cardiovascular, respiratory, abdomen, extremities, neurological, and other.

Baseline status will be summarized in Table 14.3.7.1. For each of these tests, changes from the screening to Day 3, Day 7, and Day 14 will be summarized in Table 14.3.7.2, 14.3.7.3, and 14.3.7.4, respectively.

